8.1 The participant commitment

Allied Health Professionals: 12-months (to participate in the LISTEN training, delivery, 3 online surveys, 1 phone/zoom semi-structured interview)

People with diabetes: 6-months (to participate in 3 online surveys). Participants randomised to the intervention arm will receive up to four 45-60-minute LISTEN sessions (estimate of 4-6 week per participant). It is recommended that the sessions run weekly to reinforce the skills learnt. A random sample of participants in the intervention group will also be invited to participate in a 20–30-minute semi-structured feedback interview (**Appendix 12**) via phone or videoconference (Objective 5).

Stakeholders: In addition to AHPs and people with diabetes (intervention group), key stakeholders from partner organisations will be invited to complete a semi-structured interview (via phone/video conference) at a convenient time within a four-week period. The interview will take 20-30 minutes to complete.

8.2 The project duration

2-years (please **Appendix B** for the project timeline)

8.3 Any participant follow-up

Allied Health Professionals: will be invited to complete three brief online surveys to explore satisfaction with the training program (Objective 2). The surveys will be: (1) on entry into the study (baseline/pre-training; **Appendix 6**), (2) following the LISTEN workshops (**Appendix 7**), and (3) following the completion of their supervised training (**Appendix 7**). Following delivery of the intervention during the effectiveness trial, a random sample of AHPs will be invited to complete a semi-structured interview (**Appendix 11**) to explore barriers and facilitators to the delivery of LISTEN in diabetes support services (Objective 5). Interviews will be arranged at a convenient time within a four-week period.

People with diabetes: will be invited to complete three online surveys: on entry into the study (baseline), post-intervention (8-week follow-up) and at 6-month follow-up. A random sample of intervention participants will be invited to complete a semi-structured interview (**Appendix 12**) following the intervention to explore acceptability and satisfaction with the LISTEN program, suggestions for improvement and preferences for modality to participate in the LISTEN intervention (Objective 5).

9. Data Collection/Gathering:

9.1 What information are you going to collect/gather? (as required in addition to that outlined in the HREA)

The following data will be collected:

Objective 2: Allied Health Professional Training

Observational data

During the training stage, all sessions delivered by AHPs ('training cases') will be audio-recorded and assessed for competency using the PST-PAC (**Appendix 14**) strictly for training and supervision purposes. The sessions will be reviewed by two researchers to ensure the intervention is being delivered as intended and to assess inter-rater reliability. AHPs (and 'training cases') are required to provide consent for the sessions to be recorded

Online surveys (Appendix 6 and Appendix 7)

Basic demographic and employment history.

Feedback on training. We will conduct data regarding 1) satisfaction with the program and the training as well as further training and support needs; 2) acceptability and difficulties encountered with the delivery of LISTEN; 3) suggestions for how we can improve the LISTEN training program.

Volunteer 'training cases' (adults with diabetes) will be invited to complete baseline and post-intervention (8-week follow-up) surveys (**Appendix 8**) to explore feasibility and acceptability of the outcome measures for the effectiveness trial, as well as to explore their satisfaction with the LISTEN sessions and suggestions for improving the program.

Semi structured (zoom/phone) interview (Appendix 11)

AHPs views on the barriers and enablers to delivery of LISTEN and to identify important factors for implementation and sustainability. The interview schedule is adapted from previously published research.(51)

Objective 3: Effectiveness Trial

Observational data

Program fidelity: During the trial, 20% of sessions will be audio-recorded at random. The sessions will be reviewed by two researchers to assess if the service is being delivered as intended.

We will record the number of people with diabetes recruited into the trial, ease of recruitment (i.e., the time (days) taken to recruit and enrol 454-604 consenting eligible participants), retention of participants in the program (i.e., participant completes at least one LISTEN session and declines further sessions if <4 are completed), the number of LISTEN sessions completed by participants and retention rate (i.e., proportion of enrolled participants who submit a 8 week and 6-month follow-up survey).

Online surveys (baseline, 8 weeks, and 6-month follow-up) (Appendix 9 and Appendix 10)

We will collect demographic and self-reported clinical data (e.g. age, location, type and duration of diabetes, treatment type).

At each time point, participants with diabetes will be asked questions related to their emotional wellbeing. The primary outcome, diabetes distress, will be assessed at 6-months (primary endpoint) using the Problem Area in Diabetes (PAID) scale. Secondary outcomes will include: the Kessler Psychological Distress Scale (K10)(46), emotional wellbeing (WHO-5)[48] and the Coping Self-Efficacy Scale (CSES) (47) and will be assessed at 6-months. The immediate effect (8 weeks) of the intervention will also be evaluated. Process outcomes: Self-report ratings for goal attainment (Goal Attainment Scale; **Appendix 15**) will be collected during the LISTEN sessions.

At the 8-week follow-up, participants randomised to the intervention group will be asked, using rating scales, to report on their engagement and level of satisfaction with the LISTEN sessions. Those who receive <4 sessions will be asked about their main reasons for declining further sessions.

We will also record the number of participants requiring a referral for additional mental health support, including the links and resources provided.

Objective 4: Economic evaluation

Online surveys (baseline, 8 weeks, and 6-month follow-up) (Appendix 9 and Appendix 10)

Within the randomised trial, data will be collected including the AQoL4D,(48) a generic instrument to generate quality-adjusted-life-years (QALYs). At each follow-up, all participants will complete questions about resource use and productivity impacts (absenteeism and presenteeism). Participants will be asked for consent to access their Medicare and Pharmaceutical Benefits data.

We will also record the cost of delivering LISTEN (including time required for AHPs training, supervision, delivery of the sessions).

Objective 5: Barriers and enablers

Semi-structured phone/zoom/skype interviews

To explore barriers to adoption and implementation of LISTEN, informed by the RE-AIM Framework, with key stakeholders across our partner organisations and end-users (people with diabetes).

AHPs (Appendix 11)

The interview will explore AHPs views on the barriers and enablers to delivery of LISTEN and to identify important factors for implementation and sustainability. The interview schedule is adapted from previously published research.(51)

Participating adults with diabetes (Appendix 12)

A random sample of participants allocated to the intervention group will be invited to take part in semi-structured interviews via phone/zoom. The interview schedule includes questions about program satisfaction, perceived usefulness of the program, suggestions for improving the program and preferences for delivery modality.

Key staff from partner organisations (Appendix 13)

The interview will explore views on the barriers to adoption and implementation of LISTEN, resources required to ensure sustainability and suggestions of how LISTEN can be integrated into routine practice.

9.2 Data collection/gathering techniques: How will you collect/gather the information?

We will use a combination of online surveys and semi structured interviews conducted via phone or zoom/skype as well as observational research.

9.3 Impact of and response to participant withdrawal

Participants are free to withdraw from the study at any time upon their request, for any reason. Participants who request to be withdrawn from the study will be asked to nominate, but not required to provide, a reason for withdrawal. They will be invited to voluntarily share any feedback via email. Withdrawing from the study will not affect their relationship with the researchers, the ACBRD, Deakin University, Diabetes Australia/NDSS, Diabetes Victoria and the Australian Diabetes Educators Association.

Participants will be withdrawn from the study if they are not able to be contacted following randomisation and notified of their group allocation, or if they request to withdraw at any point during the active component of the project. Participants who withdraw will be offered resources about emotional health (NDSS factsheets), links to mental health support (e.g. Beyond Blue) and recommended to speak with their primary health care provider (e.g. general practitioner).

10. Data Management:

10.1 How will you store, provide access to, disclose, use/re-use, transfer, destroy or archive the information that you collect/gather? (as required in addition to that outlined in the HREA)

ACBRD: All participant survey data (including participants' name and contact details along with their eligibility) will be stored in a database (QualtricsTM) on the Deakin University School of Psychology/ACBRD shared networked drive which will be protected by password and up to date cyber security software. Only the Deakin project members listed in the HREA will have access to this password protected Qualtrics account. At the conclusion of the study all Qualtrics data and acceptability data will be downloaded and linked according to participant unique ID. Qualtrics data will be transferred to IBM SPSS. At this stage, identifiable information (email, name) with linking participant ID will be separated from study data and stored in a password-encrypted excel spreadsheet, only accessible to Deakin University project members listed on this protocol and HREA. De-identified quantitative participant data, including participant ID, will be saved as an IBM SPSS file. Thus, the data will be re-identifiable. LISTEN session recordings between AHPs and volunteer 'training cases'/participating adults with diabetes and worksheets will be saved on the Deakin University Deakin University School of Psychology/ACBRD shared networked drive which will be protected by password and up to date cyber security software only accessible to the two Deakin researchers. Qualitative interview data (audio recorded using a computer-based recording device e.g. in-built in Zoom or Skype) will be saved on the Deakin University School of Psychology/ACBRD shared networked drive which will be protected by password and up to date cyber security software. Only Deakin University project members listed on the HREA will have access to this password protected recordings. Audio recordings containing no identifying information will be transcribed by an external professional transcribing service. De-identified data will be imported into NVivo.

Once all people who expressed interest in the study have been followed-up with and the trial is underway, the names and contact details of those not eligible to take part in the project will be deleted. All data files will be clearly labelled with the date and an accurate description of the file (e.g., yearmonthday_file description_version number). Any manipulation or changes made to the data file will be saved with a new version number (as per the above labelling guide) and previous versions retained for record. These will also be recorded and logged in e-mail correspondence.

We do not plan to post the data on a data sharing repository however we would be willing to share the data for secondary analyses with specific future researchers on request, if the project had ethics approval from a Human Research Ethics Committee and the researchers were willing to sign a Data Sharing Agreement that documents how the researchers intend to use the data and how it will be transferred, stored and disposed of. Only the anonymous data from surveys and interviews would be

provided and participants will be informed in the PLSCF of the potential that the anonymous data may be provided to other researchers for secondary analyses (**Appendix 3**).

The data will be stored on a Deakin University Secure Server for a minimum of 15 years following the final publication of the current project, after which it will be destroyed.

Include a data management plan in accordance with National Statement 3.1.45 and 3.1.56.

As per Deakin University's "code of good practice research" the data will be kept for a minimum of 15 years after the last publication of the study. This length of time has been chosen to ensure that there is time to collect all relevant data and also time to review data for publications arising from the project. After a minimum of 15 years from the date of the last publication, data will be destroyed. Information collected in digital form will be deleted (this includes: Survey program, SPSS spreadsheets, other spreadsheets, graphs, audio files, transcripts, and notes and descriptive data). All participants will be informed of how their de-identified information will be collected, stored, used, distributed, and destroyed (in the PLSCF). All surveys will be developed and distributed via Qualtrics online using the Deakin University licencing agreement. As all members of the research team have extensive experience in the field of psychology, diabetes mental health, and research design, no further training will be required to fulfil the aims of the proposed research project.

Diabetes Australia/Diabetes Victoria: Diabetes Australia and Diabetes Victoria have strict privacy and confidentiality policies, which participating AHPs will need to abide by. As part of the organisational procedures, all participating adults with diabetes allocated to the intervention group will have a case created against their name (including name and contact details). The AHPs will record that the participant (adult with diabetes) has taken part in the LISTEN program and any recommendations made by the AHP (i.e., resources or referrals to other services). The worksheet with problems/goals/actions plans etc, specific to the LISTEN program will be attached to the case notes for each individual participant. In addition, a copy will be sent to ACBRD to facilitate supervision and support of AHPs. The case records created for study participants is covered in Diabetes Victoria's Document and Records Management policy. These case notes are considered as Medical Records and are stored for 7 years after the last occasion as per the Health Records Act 2001 Schedule 1 HPP4. Principle 4—Data Security and Data Retention.

The recorded LISTEN sessions with participants will be sent to the ACBRD via a secure, encrypted email at the end of each session. Once received by the ACBRD, they will be deleted from the Diabetes Australia/Diabetes Victoria system using strict protocols. This process will follow for both the 'training cases' (Objective 2) and the trial participants with diabetes (Objective 3).

11. Data Analysis:

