Consent and screening for eligibility: People with diabetes who are interested in participating will be directed to a Qualtrics page containing a plain language statement and consent form (PLSCF). An online PLSCF will describe the purpose of the study to participants, the procedures to be followed, the risks and benefits of participation and contact details (email address and telephone number) for the research team in the event of any queries or questions. Prior to completing any study component (i.e. responding to screening questions to determine eligibility), potential participants will need to tick a box to confirm they have read and understood the PLS and consent to taking part. Participants will also be asked to sign a Services Australia consent form to access their Medicare Benefits Schedule (MBS) and/or Pharmaceutical Benefits Scheme (PBS) data. Signing this consent form is voluntary. If they decide not to sign the MBS/PBS consent form it will not affect their participation in the LISTEN Study and they will still be eligible to take part.

Following provision of informed consent, participants will be asked to complete eligibility screening questions (**Appendix 9**; see Section 7.2 for eligibility criteria and Section 13 for a summary of the screening questions). Eligibility will be automatically determined based on responses to the questions. Those who are not eligible (as determined through the screening survey) will immediately be notified and provided with links to the NDSS emotional health factsheets (practical, evidence-based resources about recognising and addressing emotional health problems: https://www.ndss.com.au/living-with-diabetes/health-management/mental-health/). Those not eligible for the project because of indications of 'severe diabetes-distress and moderate-severe symptoms of depression or anxiety' (see Section 7.2) will also be provided with links to external mental health support (e.g. Beyond Blue) and a recommendation to speak with their primary health care provider (e.g., general practitioner). The contact details for a member of the research team will be provided on the Qualtrics form should the individual wish to discuss support available.

Randomisation: Eligible participants will be directed to complete an online (pre-intervention) baseline survey. Following baseline assessment, eligible participants will be randomised to

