intervention or control (usual care), using a computer-generated program, to ensure allocation concealment. Randomisation (using stratified random permuted blocks) will be conducted in random blocks (4, 6 or 8), stratified by diabetes type, gender and age (<60; ≥60 years old). Researchers and data analyst will be blinded to group allocation.

The intervention group will receive LISTEN (1-4 weekly sessions; 45-60 minutes each), delivered via telehealth by a trained AHP.

Intervention: The core of LISTEN, problem-solving skills,³ provides participants with guidance and support to identify problems that may be contributing to their psychological distress; identify clear goals; brainstorm multiple solutions; weigh up pros and cons for each; choose a preferred solution; make a specific action plan to implement it; evaluate the outcomes from the previous session. Participants will work through up to four identified problems causing psychological distress. Participants will receive information and worksheets that will help support them between sessions and plan meaningful and enjoyable activities during the week. Strategies for working through problems that cannot be 'solved' will also be addressed. In addition, AHPs will encourage support-seeking behaviours. They will discuss how and when to seek support from mental health services, and how address their barriers for seeking support from a general practitioner or mental health professional.

[figure not shown]

Figure 1. The seven problem-solving skills in the LISTEN program⁴

Control: The control group will receive usual care including weblinks to NDSS factsheets about mental health (freely available on the NDSS website: https://www.ndss.com.au/living-with-diabetes/health-management/mental-health/), as well as links to external mental health support (e.g. Beyond blue) and if needed, a referral to their GP to discuss the best support for their emotional wellbeing. Recruitment will be primarily via the NDSS registrant database.

Outcomes: The primary outcome, diabetes distress, will be assessed at 6 months (primary endpoint) using the Problem Area in Diabetes (PAID) scale. Secondary outcomes will include: depressive and anxiety symptoms, assessed using the Kessler Psychological Distress Scale (K10),(46), emotional wellbeing (WHO-5),[48] and the Coping Self-Efficacy Scale (CSES).(47) The immediate effect (8

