³ Problem Solving Therapy is an evidence-based psychological intervention. The version of PST used in this study is based on a manualised, low-intensity version specifically developed for busy clinic settings that has been adapted for this context with the permission of the authors ([name] and [name]).

weeks) of the intervention will also be evaluated. The minimum dose (number of sessions) needed for a significant reduction of the primary outcome, and the clinical/demographic characteristics associated with dose/effect will be evaluated. Baseline demographic and clinical characteristics will be collected. Assessments will be online using Qualtrics TM. The PLSCF, screening questions and baseline survey (**Appendix 9**) and 8-week and 6-month follow-up surveys (**Appendix 10**) are attached. The surveys take 20-30 minutes to complete.

Objective 4: To evaluate the cost-effectiveness and health economic benefit of LISTEN

Methods: A within trial economic evaluation will be undertaken from health sector and partial societal perspectives. The cost to deliver the LISTEN intervention will be undertaken using financial records and micro-costing methods. Within the trial, all study participants will be asked to complete a brief resource use questionnaire at 8 weeks and 6 months to collect information about healthcare resources used and lost productivity. They will also be asked to complete the four-dimension Assessment of Quality of Life (AQoL4D) instrument,(48) a generic health related quality of life instrument that provides preference-based utility scores used to calculate quality-adjusted-life-years (QALYs). QALYs are an outcome metric combining quality and quantity of life used by health technology assessment agencies such as the Australian Pharmaceutical Benefits Advisory Committee. Participants will also be asked for consent to access their Medicare and Pharmaceutical Benefits data (**Appendix 5**).

After the trial-based economic evaluation is complete, a modelled economic evaluation is also planned. This will allow estimates of the costs and outcomes associated with LISTEN across the population of Australia and over a longer time horizon.

Objective 5: Exploring barriers and enablers to Reach, Adoption and Implementation

Methods: Semi-structured qualitative interviews, informed by the RE-AIM Framework, with key stakeholders

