11.1 How will you measure, manipulate and/or analyse the information that you collect/gather?

The primary and secondary outcomes will be measured using validated scales. Primary outcome: Diabetes distress (measured using the Problem Area in Diabetes (PAID) scale); secondary outcomes: depressive and anxiety symptoms (measured using the Kessler Psychological Distress Scale (K10), emotional well-being (measured using the WHO-5), coping self-efficacy (measured using the Coping Self-Efficacy scale). Analyses will be conducted on an intention-to-treat (ITT) basis. Repeated measures analysis of variance (ANOVA), or a mixed model analysis (residual maximum likelihood (REML) method) will be used to analyse the primary and secondary outcomes.(52) The null hypothesis, that there is no interaction between assessment time (baseline and T6 months) and trial arm (Control vs Intervention), will be tested using an F-test conducted at the 5% significance level (α =0.05). In the event that some participants have missing assessments at T6 months, the analysis of variance will be replaced by a mixed model analysis using the REML method. A per protocol set (PPS) will be defined prior to any analyses and will be used for a sensitivity analysis of the primary endpoint.

Qualitative data from semi-structured interviews will be de-identified, transcribed verbatim and imported into NVivo. Thematic analyses will be used to explore and identify key themes about participant's experiences of the LISTEN intervention, preferences for modalities and suggestions for improvement as well as perceived barriers and facilitators to adoption and implementation reported by stakeholders from partner organisations.

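### Withdrawing randomised participants who cannot be contacted ends their follow-up and is not reconciled with the intention-to-treat analysis

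*Protocol*

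**What the plan says.** Section 9.3 of the protocol names two grounds for withdrawal from the study. One is the participant's own request. The other is imposed by the study team: "Participants will be withdrawn from the study if they are not able to be contacted following randomisation and notified of their group allocation". Both lead to the same status. The section does not say whether people withdrawn for non-contact are still sent the follow-up surveys.

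The rule acts after randomisation. Section 6.1 (Objective 3) gives the order: "Following baseline assessment, eligible participants will be randomised to" intervention or usual care. The schedule of measures in section 13 places PAID at screening, with the pre-intervention survey done at the same time, so a baseline PAID score exists for everyone randomised.

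On analysis, section 11.1 says "Analyses will be conducted on an intention-to-treat (ITT) basis". If 6-month assessments are missing, "the analysis of variance will be replaced by a mixed model analysis using the REML method", and section 11.3 refers back to this. Separately, "A per protocol set (PPS) will be defined prior to any analyses"; it serves a sensitivity analysis of the primary endpoint. Neither section mentions participants withdrawn for non-contact.

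On contact and data collection, section 6.1 says "The intervention group will receive LISTEN (1-4 weekly sessions; 45-60 minutes each), delivered via telehealth by a trained AHP", while "The control group will receive usual care including weblinks to NDSS factsheets about mental health". For outcomes, "Assessments will be online using Qualtrics".

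**The concern.** Intention-to-treat has two parts: analyse people in the arm to which they were allocated, and keep measuring them whatever treatment they received. The protocol commits to the first. The non-contact rule works against the second, because it ends follow-up on an event that occurs after allocation and that the participant did not request.

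The loss is avoidable. The primary outcome is an online questionnaire, and answering it does not require that a health professional has reached the participant or that any session took place. In a pragmatic effectiveness trial, someone allocated to LISTEN who receives no session is part of the effect being estimated. The protocol already has a per-protocol set for the narrower question.

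Two things are at stake. One is precision, in a trial that already allows for 50% attrition. The other is comparability of the arms: if non-contact is more often noticed where sessions must be arranged, and those people differ in 6-month distress, the arms left with outcomes are no longer the arms that were randomised. An SAP can define the analysis set, but it cannot recover 6-month scores that were never requested.

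**Working it through.** **1. The plan's own figures on loss (section 11.4).** The evaluable total is 226 to 302 and the attrition allowance is 50%.

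- 226 / (1 - 0.5) = 452, against 454 stated (227 / 0.5 = 454)
- 302 / (1 - 0.5) = 604, as stated
- 8-week response: 143 / 198 = 72.2%, stated as 71%

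The recruitment target therefore reproduces to within 2. The 8-week response is the only observed retention figure and it pools the arms, so loss by arm cannot be estimated from the protocol.

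**2. What happens to a withdrawn participant in the planned analysis.** Section 11.1 tests the interaction between time (baseline, 6 months) and arm. A person withdrawn before week 8 has a baseline PAID score only. That score can enter the REML model, so the person need not leave the analysis set. A baseline value alone, however, carries essentially no information on the 6-month difference. The model then relies on the missing outcome being explained by the observed data. Failed contact may reflect engagement, which baseline PAID may not capture.

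**3. Illustration of possible bias (inputs assumed, not in the documents).** Let a share u of the intervention arm be withdrawn, with no such loss in control, and let their mean 6-month outcome differ by g SD from those who remain. The full-arm mean is (1 - u) × m + u × (m + g) = m + u × g, where m is the mean of those who remain. The shift is therefore u × g.

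| u | g = 0.2 SD | g = 0.3 SD | g = 0.5 SD |
|---|---|---|---|
| 5% | 0.010 | 0.015 | 0.025 |
| 10% | 0.020 | 0.030 | 0.050 |
| 20% | 0.040 | 0.060 | 0.100 |

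As a share of the 0.3 SD target: 0.010 / 0.3 = 3% up to 0.100 / 0.3 = 33%.

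If both arms lose people and g is the same in each, the shift is (u in intervention - u in control) × g:

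- 10% v 2%, g = 0.3 to 0.5: 0.08 × 0.3 = 0.024 to 0.08 × 0.5 = 0.040 SD
- 20% v 5%, g = 0.3 to 0.5: 0.15 × 0.3 = 0.045 to 0.15 × 0.5 = 0.075 SD

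With equal loss and equal g the shift is zero and only precision suffers. Under the mixed model, g should be read as the difference that remains after baseline PAID is taken into account.

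**4. Effect on arm sizes.** At u = 10% in the intervention arm only, 227 × 0.9 = 204 v 227 (N = 454), or 302 × 0.9 = 272 v 302 (N = 604). Keeping everyone in follow-up leaves the target of 454 to 604 unchanged.

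**The case against.** The strongest reply is that no contradiction is shown. Section 9.3 withdraws people from the study and says nothing about removing them from the analysis set. Section 11.1 states intention-to-treat and sends missing 6-month data to a mixed model, in which a baseline PAID score is enough to remain. The exact definition of the set is commonly left to the SAP. This stands: a reader might infer that the primary analysis becomes a modified intention-to-treat analysis, but the text does not say so. What remains is that outcome collection stops, and the choice of analysis set does not restore it.

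Second, a reader might infer that the rule removes people mainly from the intervention arm and so favours LISTEN. The rule is worded for both arms. The protocol does not say how allocation is notified, gives no counts by arm, and offers no evidence that unreached people would score worse. The difference between live sessions and weblinks makes unequal loss plausible, and no more than that. The direction is not established.

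Third, it is tempting to add this loss to the 40-50% attrition expected in section 11.4. That range comes from survey responses in a trial already running, so non-contacts may already be counted in it.

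Fourth, people who cannot be reached about their allocation may not answer surveys either, so the gain may be small. This is fair, and it limits the benefit of the change without justifying a rule that ends the attempt.

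Finally, section 9.1 already separates declining further sessions from failing to return surveys, and people with fewer than four sessions are asked for their reasons at 8 weeks. Stopping sessions is thus not treated as leaving the study. The gap concerns those never contacted.

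**Conclusion.** The point holds in a limited form. Read as written, the non-contact rule ends follow-up of randomised participants for a reason other than their own request. It creates avoidable missing outcomes and is not reconciled with the intention-to-treat commitment. It may also cause unequal loss between arms.

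The size and direction of any bias are unknown. The range of 0.01 to 0.10 SD (3% to 33% of the 0.3 SD target) is an illustration. It rests on three assumptions: that 5-20% are lost from the intervention arm only, that they differ by 0.2-0.5 SD from those who remain, and that they would otherwise have supplied outcomes. None of these comes from the protocol.

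This should be fixed, with moderate confidence. It is a rule of trial conduct, so it belongs in the protocol.

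**What to change.** Amend section 9.3 to delete non-contact as a ground for withdrawal from the study. State that every randomised participant stays in the allocated arm, that non-contact is recorded as zero sessions received, and that the 8-week and 6-month surveys are still sent unless the participant withdraws consent for follow-up. Add to section 11.1 that all participants are analysed as randomised and that non-contact is reported by arm.

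The cost is a short amendment and some extra survey reminders, possibly with a low yield. The sample size target does not change. Because the trial was already running at this protocol version, the change acts mainly prospectively and may not recover outcomes of people already withdrawn. The estimated effect may be slightly smaller, because people who never start are counted.
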